14 INTERIM ANALYSIS

An early data cut-off may be applied for the purpose for regulatory safety reporting. The date for the early data cut-off will be noted in the summary tables and in by-subject listings.

15 GENERAL PROGRAMMING SPECIFICATIONS

15.1 Format

Computer generated tables described in this analysis plan will adhere to the following specifications.

- (a) Summary tables displaying results by derived visit as defined in [Section 10.3](#).
- (b) By-subject listing will display results in chronological order of visit dates and will include both scheduled and unscheduled visits.
- (c) The estimated mean and median for a set of values will be reported to one more decimal place than the raw (observed) data and rounded appropriately. The standard errors (or standard deviations [SD]) will be reported to two additional decimal places than the raw (observed) data and rounded appropriately. For example, for age (with raw data in whole years):

N	XX
Mean (SD)	XX.X (X.XX)
LS Mean (SE)	XX.X (X.XX)
Median	XX.X
Range	XX-XX

- (d) Data in columns of a table will be formatted as follows:
 - i. Alphanumeric values will be left-justified (in mixed and upper- and lower-case)
 - ii. Whole numbers (e.g., counts) will be right justified
 - iii. Numbers containing fractional portions will be decimal aligned
- (e) All fractional numeric values will be reported with a zero to the left of the decimal point (e.g., 0.12-0.3).
- (f) Percents will be reported to one decimal place.
- (g) Dates will be reported in SAS DATE9. format (eg, 29MAR2007). Missing portions of dates should be represented on subject listings as dashes (--MAR2007). Dates that are missing because they are not

applicable for the subject should be listed as “N/A”, unless otherwise specified.

- (h) The table should be typed in Arial 10-point font. The table title should be typed in Bold Initial Caps, Arial 10-point font, beginning with the word Table X, Title.
- (i) Header (or footer) information for all tables, figures, and listings (TFLs) will include the protocol number, table status (draft or final) and the date and time the table was created.
- (j) Any TFLs generated prior to database lock or completion of TFL validation will be marked “Draft”.

15.2 Validation

All programmed tables, listings, and figures will be validated with independent programming, to include checking the log for any errors or warnings, verifying format of output against the statistical analysis plan, reviewing program output for internal consistency, consistency with other output and accuracy against the source data. Derived datasets will be independently programmed and compared using PROC COMPARE.

16 CHANGES FROM PROTOCOL SPECIFIED ANALYSES

Analysis populations names were revised to be “Enrolled Population” and “Safety Population” from protocol terminology: “*Enrolled subjects*” and “*Safety evaluable subjects (SE)*”.

For the purpose of reporting selected baseline and safety summary results, the following geographic regions were defined in the SAP: United States, Europe, Asia, and Rest of the World. The following parameters are to be reported by geographic regions: subject disposition, demographic and baseline characteristics, drug exposure, overall compliance, and overall summary of adverse events.

Laboratory results are to be reported using both standard units and conventional units.

Vital Signs: Protocol Section 12.4 indicates that for blood pressure and heart rate orthostatic results will be included. However, according to Protocol Section 9.3, these vital signs are measured after the subjects have been supine for 5 minutes

only. Therefore, SAP does not include specific summary tables for orthostatic results.

The following analyses and summary results were included in the SAP:

- Analyses for liver function test.
- number and percentage of subjects with at least one post-treatment vital sign measurement meeting pre-specified criteria were included in the SAP.
- phenytoin/phenobarbital total daily dose during titration phase by visit and overall, change and percent change from baseline, change and percent change from previous visit
- number and percentage of subjects with no change, increase, decrease in phenytoin/phenobarbital total daily dose during titration phase

17 APPENDIX 1: STUDY AS SESSMENT FLOWCHART :

Visit windows of ± 2 days allowed for Visits 3-10.	Screening	Treatment Period														End of Study Follow- up
		Titration Phase							Maintenance Phase							
Visit windows of ± 7 days allowed for all other open-label visits	Visit 1 Safety baseline	Visit 2	Visit 3	Visit 4	Visit 5	Visit 6	Visit 7	Visit 8	Visit 9	Visit 10	Visit 11	Visit 12	Visit 13	Visit 14 or Termina- tion Visit	After 1 year of treatment	Visit 15
Assessment	Day -21	Day 1	Day 15	Day 29	Day 43	Day 57	Day 71	Day 85	Day 99	Day 113	Day 143	Day 203	Day 263	Day 365	Every 3 months ^a	14 days after the last dose
Informed Consent	X															
Inclusion/ exclusion	X	X														
Demographics, medical and seizure history	X															
Vital signs ^b	X	X	X	X	X	X	X	X	X	X	X	X	X	X	X	X
Height ^c and Weight	X			X								X		X	X ^d	X
Full physical exam	X		X ^e	X ^e	X ^e	X ^e	X ^e	X ^e	X ^e	X ^e				X	X ^m	
Full neurologic exam	X													X		X
Brief neurologic exam ^d		X	X	X	X	X	X	X	X	X	X	X	X		X	
C-SSRS ^e	X	X	X	X	X	X	X	X	X	X	X	X	X	X	X	X

Visit windows of ± 2 days allowed for Visits 3-10.	Screening	Treatment Period														End of Study Follow-up
		Titration Phase							Maintenance Phase							
Visit windows of ± 7 days allowed for all other open-label visits	Visit 1 Safety baseline	Visit 2	Visit 3	Visit 4	Visit 5	Visit 6	Visit 7	Visit 8	Visit 9	Visit 10	Visit 11	Visit 12	Visit 13	Visit 14 or Termination Visit	After 1 year of treatment	Visit 15
Assessment	Day -21	Day 1	Day 15	Day 29	Day 43	Day 57	Day 71	Day 85	Day 99	Day 113	Day 143	Day 203	Day 263	Day 365	Every 3 months ^a	14 days after the last dose
ECG ^f	X													X	X ^m	
Serum pregnancy test ^g	X															X
Urine pregnancy test ^g		X			X				X		X	X	X	X	X ^r	
Clinical Laboratory safety assessment ^h	X		X	X	X	X	X	X	X	X		X	X	X	X ^l	X
Urinalysis	X													X	X ^m	
Concomitant medication	X	X	X	X	X	X	X	X	X	X	X	X	X	X	X	X
Drug accountability			X	X	X	X	X	X	X	X	X	X	X	X	X	X
Dispense study drug		X	X	X	X	X	X	X	X	X	X	X	X	X	X	
Adverse events		X	X	X	X	X	X	X	X	X	X	X	X	X	X	X
YKP3089 PK Draw ⁱ							X	X								

Visit windows of ± 2 days allowed for Visits 3-10.	Screening	Treatment Period														End of Study Follow-up
		Titration Phase							Maintenance Phase							
Visit windows of ± 7 days allowed for all other open-label visits	Visit 1 Safety baseline	Visit 2	Visit 3	Visit 4	Visit 5	Visit 6	Visit 7	Visit 8	Visit 9	Visit 10	Visit 11	Visit 12	Visit 13	Visit 14 or Termination Visit	After 1 year of treatment	Visit 15
Assessment	Day -21	Day 1	Day 15	Day 29	Day 43	Day 57	Day 71	Day 85	Day 99	Day 113	Day 143	Day 203	Day 263	Day 365	Every 3 months ^a	14 days after the last dose
Phenytoin or phenobarbital PK draw ^d		X ^a		X	X	X	X	X								
Concomitant AED PK Draw ^k		X ^a						X	X							
EEG and MRI or CT scan ^o	X															
Follow up calls		X ^a	X ^a	X ^a	X ^a	X ^a	X ^a	X ^a	X ^a							
Dispense Laminated Safety Card		X	X	X	X	X	X	X	X							

C-SSRS = Columbia Suicide Severity Rating Scale; ECG = electrocardiogram; AED = antiepileptic drug; PHT = phenytoin; PB = phenobarbital.

- a. After 12 months of participation in the open-label extension phase, subjects will be re-evaluated. Those who are benefiting from treatment with YKP3089 may continue use of the drug at the discretion of the investigator, until development is stopped by SK Life Science Inc, or the product is approved for marketing, or anytime at the discretion of SK Life Science Inc.
- b. Vital signs include blood pressure, heart rate (supine for 5 minutes), temperature, and respiratory rate.
- c. Height measured only at Visit 1.
- d. Brief neurological exam should be done only if symptoms require
- e. Administer the Baseline/Screening version of the C-SSRS at Screening. Administer the Since Last Visit version at all subsequent visits.
- f. 12-lead ECG will be performed once. Additional ECGs should be performed at any other time if clinically indicated.

- g. For female subjects of childbearing potential: If pregnancy is suspected at any time during the study, an interim test may be performed in addition to scheduled assessment.
- h. Laboratory assessment: Safety assessment includes blood chemistry and hematology. If the subject meets an exclusion criterion at Visit 1, an unscheduled laboratory sampling can be repeated for confirmation.
- i. Two blood samples will be collected for the determination of YKP3089 plasma levels: For patients that are taking YKP3089 in the morning and coming into the visits in the morning, the first blood draw will be collected upon subjects' arrival to the study unit; the second blood draw should be collected within 30 minutes to 2 hours after the medication is taken. Collect at visit 8 and/ or 9 depending on stability of dosing (doses must be stable for 2 weeks prior to these visits) of all concomitant AEDs including oxcarbazepine, topiramate, lamotrigine, lacosamide, clobazam, perampanel, levetiracetam, phenytoin and phenobarbital and YKP3089. YKP3089 PK draw is applicable for subjects on phenytoin and phenobarbital globally and all subjects at US sites.
- j. At Visit 2, a single trough level of phenytoin or phenobarbital will be obtained. At visits 4, 5, 6, 7 and 8 two blood samples will be collected for the determination of phenobarbital and phenytoin plasma levels: For subjects that are taking phenytoin or phenobarbital in the morning and coming into the visits in the morning, the first blood draw will be collected upon subjects' arrival to the study unit; the second blood draw should be collected within 2 to 4 hours after the medication is taken.
- k. Concomitant AED PK draw will be done at US sites only. At Visit 2, a single trough level of concomitant AEDs will be obtained. At Visits 8 and 9, two blood samples will be collected for the determination of concomitant AED plasma levels: For subjects that are taking concomitant AEDs in the morning and coming into the visits in the morning, the first blood draw will be collected upon subjects' arrival to the study unit; the second blood draw should be collected within 30 minutes to 2 hours after the medication is taken. For patients that are taking concomitant AEDs in the afternoon and/or coming into the visits in the afternoon, the first blood draw will be collected upon subjects' arrival to the study unit; the second blood draw should be collected within 30 minutes to 2 hours after the first blood draw with timing of the dose, blood draws and strength of previous dose clearly documented. Collect at visit 8 and/ or 9 depending on stability of dosing (doses must be stable for 2 weeks prior to these visits) of concomitant AEDs and YKP3089 for subjects on concomitant AEDs other than phenytoin or phenobarbital. Concomitant AEDs levels will be obtained only for oxcarbazepine, topiramate, lamotrigine, lacosamide, clobazam, perampanel and levetiracetam.
- l. Every 6 months after Visit 14.
- m. Every 12 months after Visit 14.
- n. Sites must instruct the subject and schedule the visit accordingly to obtain a trough level. Also the blood must be collected before first dose of YKP3089.
- o. If a CT or MRI has not been performed within the last 10 years, one must be performed prior to Visit 2. If an EEG report cannot be obtained, and the subject is otherwise eligible, an EEG may be performed
- p. At visit 1, 14, and yearly thereafter, full physical. At visit 3-10, limited physical exam to identify evidence of hypersensitivity signs such as rash, swelling, lymphadenopathy and fever.
- q. Site calls to subjects at least once in between the clinic visits to remind them to be vigilant regarding signs and symptoms of DRESS
- r. Every 3 months after Visit 14

18 APPENDIX 2: DATA HANDLING RULES FOR MISSING OF PARTIAL START/STOP DATES FOR CONCOMITANT MEDICATIONS, CONCOMITANT AEDS, AND BASELINE AEDS

Concomitant Medications and Concomitant AEDs

If a concomitant medication or AED, as reported on the eCRF, has a partially or completely missing start or end date, use the following algorithm to impute missing components of the date(s). Imputed dates will be used in order to determine prior/concomitant status of a medication.

If a medication has some missing components in both the start and end dates, first impute the end date as follows (only if the medication is not ongoing):

1. If CMENDTC contains only year and month – impute the missing day to the last day of the corresponding month (e.g., 31 for January, or 30 for April) or date of data cut-off (whichever comes first).
2. If CMENDTC contains only year – impute the missing day and month to the 31st of December of the corresponding year or date of data cut-off (whichever comes first).
3. If CMENDTC is completely missing impute to the date of end of the last period/phase defined for the subject or date of data cut-off (whichever comes first).

Note: The end date should remain null for medications that are ongoing.

After having imputed the end date (if needed), impute the therapy start date if it is partial or missing as follows:

4. If CMSTDTC contains only year and month – impute the missing day to the 1st day of the corresponding month.
5. If CMSTDTC contains only year – impute the missing day and month to the 1st of January of the corresponding year.
6. If CMSTDTC is completely missing impute to the date of start of the screening period (of IFC date) or to the medication end date (previously imputed if needed), whichever is earlier.

Baseline AEDs

Baseline AEDs are AEDs that started prior to and are ongoing at the time of the first dose of study medication.

Any AEDs recorded as “prior” in eCRF will be evaluated if it is a baseline AED or not.

- (1) If both start and stop dates are missing, the medication will not be considered as Baseline AEDs and will not be counted in number of baseline AEDs.
- (2) If an AED is identified as Prior in eCRF and it is “not ongoing” and has partial end date, the following rules will be applied:
 - if CMENDTC contains only year or day -year and year < first dose date year, the medication will not be considered Baseline AED
 - if CMENDTC contains only year or day-year and year >= first dose date year, the medication will be considered Baseline AED
 - if CMENDTC contains only month-year and month-year < first dose date month-year, the medication will not be considered Baseline AED
 - if CMENDTC contains only month-year and month-year >= first dose date month-year, the medication will be considered Baseline AED
 - if CMEDTC contains only day-month (ie, no year), the medication will not be considered Baseline AED
- (3) If AEDs are not recorded as “prior” in eCRF, the following rules will be considered if start dates are missing or have partial dates:
 - If CMSTDTC contains only year and month – impute the missing day is the 1st day of the corresponding month.
 - If CMSTDTC contains only year – impute the missing day and month to the 1st of January of the corresponding year.
 - If CMSTDTC is completely missing impute to the date of start of the screening period (of IFC date).
- (4) After AED start date is imputed:
 - If the imputed start date > the first dose date, AED will not be considered “prior” AED and will not be considered Baseline AED

- If the imputed start date \leq the first dose date, AED will be considered “Prior” AED and will be evaluated as potential Baseline AED. The decision if AED is Baseline AED will be based on CMENDTC [as per rule (2) above].

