9.4 Pharmacokinetic Evaluations

Time and date of each blood draw and dosing records (time/date/dose) of YKP3089 and AEDs prior to each blood draw will be recorded on the eCRF and other appropriate forms.

Plasma samples will be assayed for YKP3089 and AEDs at a specified bioanalytical laboratory using previously validated methods. Assay methodology will be detailed in separate assay protocols.

For subject taking phenytoin or phenobarbital

These samples will be obtained from subjects taking phenobarbital or phenytoin at any global sites.

At Visit 2, a single trough level of phenytoin or phenobarbital will be obtained. At Visits , 4, 5, 6, 7 and 8, two blood samples will be collected for the determination of phenobarbital or phenytoin plasma levels: For the subjects taking phenytoin or phenobarbital in the morning and coming into the visits in the morning, the first blood draw will be collected upon subjects' arrival to the study unit; the second blood draw should be collected within 30 minutes to 2 hours after the medication is taken. At Visits 8 and 9, two blood samples will be collected for YKP3089 depending on stability of dosing (stable dose all AEDs including YKP3089 for prior 2 weeks).

For subject taking concomitant AEDs other than phenytoin or phenobarbital

These samples will be obtained from subjects taking concomitant AEDs other than phenobarbital or phenytoin at US sites only.

At Visit 2, a single blood sample will be drawn to determine trough level if the subject is taking one of the followings, oxcarbazepine, topiramate, lamotrigine, lacosamide, clobazam, perampanel and levetiracetam. At Visit 8 and/or 9, two blood samples will be drawn from the same subjects to determine plasma levels of YKP3089, oxcarbazepine, topiramate, lamotrigine, lacosamide, clobazam, perampanel and levetiracetam. Collect at visit 8 and/ or 9 depending on stability of dosing (stable dose all AEDs including YKP3089 for prior 2 weeks). At Visit 8 and 9, for the subjects that are taking concomitant AEDs in the morning and coming into the visits in the morning, first blood draw will be collected upon subjects' arrival to the study unit; the second blood draw should be collected within 30 minutes to 2 hours after the medication is taken. For

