patients that are taking concomitant AEDs in the afternoon and/or coming into the visits in the afternoon, the first blood draw will be collected upon subjects' arrival to the study unit; the second blood draw should be collected within 30 minutes to 2 hours after the first blood draw with timing of the dose, blood draws and strength of previous dose clearly documented.

The collection schedule is summarized in [Table 11](#) below.

Table 11. Blood Collection Schedule* for YKP3089 and AED Levels

Cohort →	Subjects taking Phenytoin or Phenobarbital	Subjects taking AEDs other than Phenytoin or Phenobarbital –US sites only
Blood collection for YKP3089 levels	Visits 8 and/or 9	Visits 8 and/or 9
Blood collection for phenytoin or phenobarbital levels	Visits 2*, 4, 5, 6, 7 and 8	Not Applicable
Blood collection for concomitant AEDs (other than phenytoin or phenobarbital) levels	None	Visits 2*, 8 and/or 9

* At Visit 2, one sample will be collected; at all other visits, two samples will be collected

Additional Samples

Additional blood samples may be drawn for levels of concomitant AEDs during the open label maintenance phase if the investigator believes that symptoms of toxicity may be related to concomitant AEDs.

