12.5 Pharmacokinetics and Pharmacodynamics Analysis

YKP3089 plasma concentration data collected from this study will be pooled with data from other YKP3089 clinical trials for possible population pharmacokinetic and pharmacodynamic analysis. An integrated population pharmacokinetic model for YKP3089 will be developed. Standard population pharmacokinetic parameters (eg, total body clearance, CL/F) in epilepsy patients and their inter- and intra-individual variability will be estimated. The effects of demographic characteristics, concomitant medication including AEDs, laboratory values, and other subject covariates on YKP3089 pharmacokinetics will be evaluated.

For phenytoin, phenobarbital plasma concentrations obtained during titration phase (Visits 3-6) will be compared with that taken at baseline (Visit 2) to assess the effect of YKP3089 on these two AEDs. The timing of AED sampling in relation to the subject's AED dosing schedule will be factored into the analysis.

For each concomitant AED (oxcarbazepine, topiramate, lamotrigine, lacosamide, clobazam, perampanel and levetiracetam only), plasma concentrations obtained at Visits 8 and or 9 will be compared with that taken at baseline (Visit 2) to assess the effect of YKP3089 on these 7 AEDs. The timing of AED sampling in relation to the subject's AED dosing schedule will be factored into the analysis.

If warranted, the AED plasma concentration data collected from this study will be pooled with data from other YKP3089 studies to assess the potential for an interaction with YKP3089. Results will be displayed descriptively in tabular form.

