1 REVISION HISTORY

Versi on	Date	Author	Description
1.0	25Sep2017	QDS	Based on Protocol Amendment 3
2.0	19Jun2018	QDS	Updated per Protocol Amendment 4 and additional requests from SKLSI after meeting with FDA
3.0	26Jul2018	QDS	Clarifications for Physical Exam, C-SSRS visit windows. Updated definition for duration of epilepsy. Removed analyses for overall compliance. Administrative changes for subjects disposition, clinical laboratory tests, vital signs analyses
4.0	23Aug2018	QDS	Removed reference to Screen Failures as an analysis population. Removed all analyses by country and region. PK Section: AED plasma concentration analysis will be based on Central Lab results Included Study Assessment Flowchart from Protocol Amendment 4 in Appendix 1
5.0	05Sep2018	QDS	Updated analyses for LFTs to include all baseline values (ie, not restricted to normal baseline)

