9 STUDY SUBJECTS

9.1 Determination of Sample Size and Randomization

No formal sample size estimation was involved for this long-term safety study. At least 20 subjects taking phenytoin and at least 20 subjects taking phenobarbital are planned to be enrolled. Additional subjects taking AEDs other than phenytoin or phenobarbital will be enrolled in order to expose at least 1,000 subjects for 6 months to further evaluate long term safety.

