Plasma concentrations of YKP3089 and of concomitant AEDs measured in samples collected in this study will be combined with clinical data from previous studies to generate and validate population pharmacokinetic model for YKP3089. Relevant concomitant AEDs will be tested as covariates to evaluate their possible effect on YKP3089 PK. In addition, the effect of YKP3089 on the PK of relevant AEDs (like lamotrigine or lacosamide for instance) will be assessed if deemed appropriate. These analyses will be included in the separate report.

For the CSR, summary tables including descriptive statistics (mean, SD, median, minimum, maximum) for plasma concentrations of the concomitant AEDs and for plasma concentrations of the YKP3089 as per Central Lab results will be prepared by the planned collection timepoints.

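### The flow chart and the protocol text give different times for the second phenytoin/phenobarbital sample (2 to 4 h versus 30 min to 2 h after the dose), and the SAP tables by planned timepoint cannot separate them

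*SAP*

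**What the plan says.** **Flow chart.** Footnote j in SAP Appendix 1 covers the two phenytoin/phenobarbital samples at Visits 4 to 8. For subjects who dose and attend in the morning, the first is taken on arrival and "the second blood draw should be collected within 2 to 4 hours after the medication is taken". The SAP revision history (version 4.0) gives the origin of the chart: "Included Study Assessment Flowchart from Protocol Amendment 4 in Appendix 1".

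**Protocol text.** Section 9.4 covers the same two samples at the same visits in the same subjects and says "the second blood draw should be collected within 30 minutes to 2 hours after the medication is taken". The visit lists in 9.1.4, 9.1.5, 9.1.6 and 9.1.7 (Visits 4, 5, 6 and 7) give that same shorter window. Protocol Table 11 schedules phenytoin/phenobarbital levels at "Visits 2*, 4, 5, 6, 7 and 8", with one sample at Visit 2 and two at every other visit.

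**Analysis.** Protocol 12.5 plans to compare titration-phase concentrations with the Visit 2 baseline and says that sample timing relative to AED dosing will be taken into account. It gives no method. SAP 12 repeats the sampling visits without a window for the second draw. It commits the study report to descriptive concentration tables that "will be prepared by the planned collection timepoints". Protocol 9.4 and SAP 12 both have actual dose and draw times recorded on the eCRF.

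**The concern.** A plasma concentration after an oral dose depends on the time since that dose. If some sites draw the second sample early and others late, a table row labelled only by visit and draw number combines concentrations from different parts of the dosing interval. A difference between visits could then partly reflect which text the contributing sites followed. These tables serve the first two study objectives, the phenytoin and phenobarbital interactions with YKP3089. The cohorts are small: "At least 20 subjects taking phenytoin and at least 20 subjects taking phenobarbital are planned to be enrolled". With about 20 subjects per drug, a few sites working to a different window could affect a by-visit summary.

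**Working it through.** **Are both texts current?** Yes. The SAP is written against Protocol Amendment 4, and its revision history says the flow chart comes from that amendment. Amendment 5 lists only version, date and address updates. The conflict does not rest on an amendment log.

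**Do they govern the same draw?** Yes. Both concern the second phenytoin/phenobarbital sample, at Visits 4 to 8, in subjects dosing and attending in the morning, timed from intake of the medication. The Visit 8 list is incomplete in the copy I had, but Protocol 9.4 names Visit 8. Footnotes i and k of the same chart, for YKP3089 and the other AEDs, use 30 minutes to 2 hours for morning dosing, so footnote j differs from its neighbours as well.

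**Windows as intervals (hours since dose).**
- Protocol text: [0.5, 2]. Footnote j: [2, 4].
- Overlap = min(2, 4) − max(0.5, 2) = 2 − 2 = 0 h. Only the 2 h endpoint is shared.
- Midpoints: (0.5 + 2)/2 = 1.25 h and (2 + 4)/2 = 3.0 h.
- Largest separation between two draws that each comply with one text: 4 − 0.5 = 3.5 h.

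**Draws under the conflicting rule.** Inputs: at least 20 + 20 = 40 subjects (SAP 9.1), five two-sample visits (Protocol Table 11) and one second draw per visit. Assumptions: minimum enrolment, full attendance, and everyone dosing and attending in the morning.
- Second draws at Visits 4 to 8: 40 × 5 = 200.
- All post-baseline phenytoin/phenobarbital draws: 40 × 5 × 2 = 400, so half are affected.
- Protocol 12.5 names Visits 3 to 6 for its comparison. Only Visits 4 to 6 of these are sampled: 40 × 3 = 120.
- Protocol 8.3 lets subjects taking phenobarbital once daily at bedtime keep that schedule. If all 20 phenobarbital subjects did so, the count would fall to 20 × 5 = 100. Missed visits lower it further; enrolment above the minimum raises it.

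**Does the analysis plan correct for timing?** SAP 4 says the SAP supersedes the protocol's statistical considerations. SAP 12 does not carry over the timing commitment, and SAP 16 does not list its omission as a change. The separate population PK report is committed to a YKP3089 model. It covers the effect of YKP3089 on other AEDs only where judged appropriate, with lamotrigine and lacosamide as the examples. Nothing in the SAP therefore commits to a time-adjusted phenytoin or phenobarbital summary.

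**Size of any bias.** The documents give no absorption or elimination figures for phenytoin or phenobarbital, so the concentration difference between the windows cannot be calculated.

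**The case against.** The strongest reply is that the data can be recovered and the effect is unproven. Dose and draw times are recorded, Protocol 12.5 commits to using them, the tables are descriptive with no inferential analysis (SAP 10.1), and no rule excludes a sample for its timing. The arrival draw at each visit and the Visit 2 trough are untouched. Baseline is itself a trough, so a post-dose second sample is not like-for-like with it under either window, and settling on one window would not cure that.

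Most of this stands, and it limits the point. It does not dispose of it, because the timing commitment was not carried into the document that governs the analysis, and the only tables promised are blind to actual time.

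A reader might infer that the samples do mix the two windows, or that at least 200 of them are mistimed. The documents support neither. They show two rules that sites could follow, not what sites did, and I could not read the protocol's own Table 1. The figure of 200 counts draws subject to the conflict under favourable assumptions; it is neither a floor nor a count of errors.

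**Conclusion.** The contradiction is real, and both sides are current text. Second samples can come from two windows that share only the 2 h point and can differ by up to 3.5 h since dose. With 40 subjects, full attendance and all-morning dosing, 200 of 400 post-baseline draws are exposed, 120 of them at Visits 4 to 6. The by-visit tables planned in SAP 12 would neither reveal nor adjust for a mixture.

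It would go too far to say that the interaction results are biased: the documents give no basis for the direction or size of an effect. This should be corrected. Because actual times are on the eCRF, it can still be handled in the analysis even for samples already drawn.

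**What to change.** 1. Reconcile footnote j of the flow chart with Protocol 9.1.4 to 9.1.7 and 9.4 so that one window applies. This review takes no position on which window is right.
2. In SAP 12, restore the Protocol 12.5 commitment. Alongside the planned-timepoint tables, add a descriptive summary of phenytoin and phenobarbital concentrations by actual time since the last dose of that AED. Fix the time categories before the concentrations are tabulated. They must cover every draw, including those from evening dosers and those beyond 4 h; splitting only at the two stated windows would leave samples out.

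**Cost.** No new data are needed. The SAP change is a sentence or two and one more table, whose cells will be small in cohorts of about 20. Correcting the protocol text goes through the normal amendment process, with the ethics committee or IRB approval that Protocol 13.6 requires.
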